6.1 Inclusion Criteria and Exclusion

To be included in the trial the patient must:

- Have given written informed consent to participate
- Be aged 18 years and over
- Have IBD and anemia

Whenever the inclusion criteria are satisfied, the patient can be included in the study since there are no exclusion criteria.

Patients can be participating in other research, either, observational, interventional or other drug research concerning the treatment of IBD. Patients with IDA can also participate in the companion study RIRART II that will compare three iron supplementation regimens in terms of efficacy and safety.

6.2 Subject withdrawal criteria

At anytime during the study, participating subjects may ask to be withdrawn from the study. Withdrawn subjects can be followed up for their IBD at the same participating Center where they were initially enrolled. Withdrawn subjects will not be replaced.

7 Concomitant therapy

Nutritional supplementation with iron and/or vitamin integrators containing folic acid or vitamin B12, as well as any other treatment of IBD and relative comorbidities are allowed during the study.

8 Procedures and assessments

Laboratory assessments can be performed outside the participating Centers, and results faxed or emailed to the Investigators who will register data in the eCRF. Result notification to the trial team must be performed as soon as possible.

8.1 Screening evaluation

8.1.1 Screening Assessments

Study-related specific assessments will only be conducted after subjects have given written informed consent.

8.1.2 Subject Registration

Subjects will be registered locally and assigned a registration number/code. This number, together with the Center code, will constitute the unique patient identification code. In the trial documentation the patient must be always identified by means of this code, and only the patient physicians must be able to identify the patient from the assigned code.

8.2 Baseline assessments

All patients will have a full medical history taken and a clinical examination. The following data points are to be recorded:

- a) Weight in Kg
- b) Gender
- c) Age and date of birth
- d) Any significant past medical history
- e) CDAI and CAI disease activity scores for Crohn's disease and ulcerative colitis respectively
- f) Full blood count (including platelets and differential white cell count)
- g) Biochemical series: including creatinine, serum iron, transferrin, serum ferritin, C reactive protein (PCR), folic acid, vitamin B12 (these are mandatory; further biochemical parameters useful for the study are reported in the CRF)
- h) IBDQ score, VAS evaluation of fatigue
- i) Actual treatment

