CDAI	Crohn disease activity index
CRF	Case Report Form
CTQT	Clinical Trial Quality Team
DMC	Data Monitoring Committee
DSUR	Development Safety Update Report
GCP	Good Clinical Practice
GP	General Practitioner
Hb	Hemoglobin
IBDQ	Inflammatory bowel disease questionnaire
IDA	Iron deficiency anemia
IG-IBD	Gruppo Italiano per lo Studio delle Malattie Infiammatorie Croniche Intestinali
IMP	Investigational Medicinal Product
MHRA	Medicines and Healthcare products Regulatory Agency
NIMP	Non Investigational Medicinal Product
RA	Regulatory Agency
R&D	Research and Development
REC	Research Ethics Committee
SAE	Serious Adverse Event
SUSAR	Suspected Unexpected Serious Adverse Reaction
TMG	Trial Management Group
TSC	Trial Steering Committee
UC	Ulcerative colitis
VAS	Visual analogue scale

3 Trial Flow Chart

4 Introduction

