5.1 Statement of design

We will perform a longitudinal, prospective, observational study whose aim is the determination of the prevalence and pathogenesis of anemia in IBD patients. Anemia is defined according to WHO criteria: Hb <13.0 g/dL for males and Hb <12 g/dL for females (Blanc et al, 1968). Anemia work-up should be initiated whenever Hb concentration is below normal and will include the determination of the laboratory parameters reported in the CRF. A serum ferritin <100 µg/L and transferrin saturation <20% are required for the diagnosis of isolated IDA and for the association of IDA and inflammation.

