6.5.2 Secondary objectives

Secondary objectives of the study are a) to investigate the pathogenesis of anemia in IBD, with a particular focus on the differential diagnosis between IDA and AI, and how disease activity, extension or behavior influence the relative frequency of IDA and AI; b) to verify the adherence to ECCO guidelines for the treatment of IDA in IBD (the proportion of patients with IDA that receive adequate iron supplementation); c) to administer dedicated questionnaires to the patients in order to measure the influence of anemia on fatigue and quality of life among IBD patients.

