8.6 Schedule of Assessments

A format of all study-related assessments is included in the CRF.

9 Evaluation of Results (Definitions and response/evaluation of outcome measures)

The primary end-point of the observational study (prevalence of anemia) will be evaluated at patient recruitment. Other informations concerning laboratory parameters, quality of life and clinical course will be collected at the scheduled follow-up visits.

10 Statistical methods and number of Subjects to be enrolled

If at least 60 IG-IBD Centers will participate to the study, 5000 to 8000 IBD patients will be screened for anemia within 6 to 12 months from the start of the study. Since anemia affects 25% to 40% of IBD patients, we expect to include 2,000 anemic patients for this observational study. For the first endpoint (the prevalence of anemia) the precision that can be obtained, based on this hypothesis, is summarized in Table 2. Approximately 80 to 90% of these patients will have some form of iron deficiency and/or AI. This will allow to evaluate differences in prevalence of IDA and AI according to gender, age, diagnosis, time from diagnosis, presence of inflammation, disease activity, extension and behavior, and to evaluate variables associated with type and severity of anemia in both univariate and multivariate analysis.

Multivariable models will be fitted to assess the role of anemia on the outcome, while adjusting for potential confounders. Linear regression, logistic regression or Poisson regression models will be used depending on the outcome distributions. Descriptive statistics will be computed overall and by anemia groups.

11 Definition of the end of the study

The competent authority and Ethics Committee will be notified of the end of the clinical study within 90 days of its completion. The end of study will be the date of the last patient's last visit.

12 Data handling and record keeping**13.1 CRF**

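### In Crohn's patients, the CDAI (if the standard version with a hematocrit item) builds in part of any association between disease activity and severity of anemia

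*Protocol*

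**What the plan says.** Section 6.1 admits patients who "Have IBD and anemia". Section 5.1 defines anemia by hemoglobin: "Hb <13.0 g/dL for males and Hb <12 g/dL for females".

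Activity is measured at baseline (section 8.2, item e) by "CDAI and CAI disease activity scores", the first in Crohn's disease and the second in ulcerative colitis. The abbreviation list expands CDAI only as "Crohn disease activity index". No items, weights or version are given for either score, and no version without a blood-count item is mentioned.

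Activity is then put to analytical use:

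- The secondary objectives (numbered 6.5.2) ask "how disease activity, extension or behavior influence the relative frequency of IDA and AI".
- Sections 5.3 and 10 list disease activity among the factors by which the prevalence of IDA and AI will be compared. They add that the sample will allow the trial "to evaluate variables associated with type and severity of anemia in both univariate and multivariate analysis".
- Section 10 also plans multivariable models for the role of anemia, adjusted for potential confounders that it does not name.

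Type of anemia is defined by iron markers. Section 5.1 states: "A serum ferritin <100 µg/L and transferrin saturation <20% are required for the diagnosis of isolated IDA". Table 1 also uses only ferritin and transferrin saturation.

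**The concern.** A score that contains a measure of red-cell mass is not a separate variable from severity of anemia. If the CDAI adds points as hematocrit falls, a Crohn's patient with lower Hb scores as more active even with identical bowel symptoms. An analysis of activity against severity would then find an association when bowel disease has no effect on Hb, and a larger sample would only make that association look firmer.

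The same overlap matters if the full CDAI is an adjustment variable in models of anemia on fatigue or quality of life. Holding the total fixed, a patient with lower Hb must have fewer symptom points, so the comparison sets anemia against a symptom deficit and understates its effect.

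**Working it through.** **The plan's own figures.** The protocol gives no figure for activity against anemia. Its only precision figures, in Table 2, concern prevalence and reproduce. For 5000 screened at 25%, 1.96 × √(0.25 × 0.75 / 5000) = 1.2 points, giving 23.8 to 26.2 and a width of 2.4, as stated. They do not bear on this point.

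**Inputs from the protocol.** CDAI in Crohn's disease (8.2). All enrolled patients have Hb below 13.0 (men) or 12 (women) g/dL (5.1, 6.1).

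**Assumptions not in the protocol.**
- Hematocrit item = 6 × (47 − Hct) in men and 6 × (42 − Hct) in women.
- Hct = 3 × Hb, with 3.2 × Hb as a variant.
- SD of Hb among enrolled patients 0.8 to 1.5 g/dL.
- SD of the remaining CDAI items 60 to 100 points, unrelated to Hb.

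**Step 1: points per g/dL.** 6 × 3 = 18, or 6 × 3.2 = 19.2 under the variant.

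**Step 2: spread of the item within the cohort (Hct = 3 × Hb).**

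| | Just below threshold | Hb 10 | Hb 8 |
|---|---|---|---|
| Men | 6 × (47 − 38.7) = 49.8 (Hb 12.9) | 102 | 138 |
| Women | 6 × (42 − 35.7) = 37.8 (Hb 11.9) | 72 | 108 |

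The item thus varies by 88.2 points in men (138 − 49.8) and 70.2 in women (108 − 37.8) over these Hb ranges.

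**Step 3: built-in correlation with severity.** With the other items unrelated to Hb, r = 18 × SD(Hb) / √[(18 × SD(Hb))² + SD(rest)²].
- Lowest: SD(Hb) 0.8, SD(rest) 100: 14.4 / √(14.4² + 100²) = 0.14.
- Middle: SD(Hb) 1.0, SD(rest) 80: 18 / √(18² + 80²) = 0.22.
- Highest: SD(Hb) 1.5, SD(rest) 60: 27 / √(27² + 60²) = 0.41.

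With 19.2 points per g/dL, the ends become 15.36 / √(15.36² + 100²) = 0.15 and 28.8 / √(28.8² + 60²) = 0.43.

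The Crohn's share of the 2,000 patients is not stated. If it were 500 to 800, a correlation of 0.14 would give a Fisher z statistic of about 0.141 × √497 = 3.1 to 0.141 × √797 = 4.0. Even the smallest value would then be declared significant.

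**Step 4: adjustment for the full score.** Let A be the CDAI without the item. Within a sex, CDAI = A + constant − 18 × Hb. If an outcome depends on bh × Hb + ba × A, substituting A = CDAI − constant + 18 × Hb makes the Hb coefficient in the model with the full CDAI equal to bh + 18 × ba. If fatigue is worse at lower Hb (bh negative) and at higher activity (ba positive), the two terms have opposite signs and the anemia effect is pulled toward zero. For a quality-of-life score where higher is better, both signs flip and the result is the same. Each 0.01 outcome units per CDAI point moves the Hb coefficient by 18 × 0.01 = 0.18 units per g/dL.

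**Step 5: type of anemia.** Neither ferritin nor transferrin saturation enters the assumed item. The built-in CDAI difference between types is 18 × (difference in mean Hb): 0 if there is none, 5.4 at 0.3 g/dL, 9 at 0.5 and 18 at 1 g/dL. The protocol gives no mean Hb by type.

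**The case against.** The best reply is that the protocol neither describes the hematocrit item nor says that activity will be analysed against severity. The clause on severity names no variable, and activity is not named as a confounder. Score derivation and covariate choice commonly belong in the SAP, which is not at hand. The CRF is not at hand either and may already hold the items. Section 8.2 collects a full blood count, so the item could be subtracted later, and CRP and presence of inflammation give other views of activity.

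Much of this stands. The item is an assumption about the instrument, the severity analysis is the natural reading rather than a named one, the adjustment problem is conditional, and no data are irretrievably lost. But section 8.2 does choose the instrument and asks for scores, not items. Nothing in the protocol warns that this score shares content with anemia.

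A reader might infer more than the document supports:

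- **That the entry criterion itself creates the association.** It only raises every score. Variation in Hb among enrolled patients does the work.
- **That the secondary objective on IDA versus AI is necessarily biased.** Type is defined without Hb, so the effect is zero unless mean Hb differs between types.
- **That ulcerative colitis is equally affected.** The CAI version is not stated, so nothing can be concluded.
- **That anemia alone reliably turns quiet disease into active disease.** Take an assumed cut-off of 150 and a man with Hb 10 and 50 points from other items. He scores 50 + 102 = 152 with Hct = 3 × Hb, but 50 + 6 × (47 − 32) = 140 with 3.2 × Hb. The classification reverses with the ratio chosen.

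**Conclusion.** The point holds for Crohn's patients and for severity of anemia. If the CDAI is the standard version, about 18 to 19 points per g/dL of Hb are mechanical. This gives a built-in correlation with severity of about 0.14 to 0.41 under the stated SDs and 18 points per g/dL. If the full CDAI is also used to adjust models of anemia on fatigue or IBDQ, the anemia effect is biased toward zero under the signs assumed above. Neither bias shrinks with sample size.

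Both results rest on the assumed item weights, the hematocrit-to-Hb ratio and the assumed SDs; the correlation also takes the other items to be unrelated to Hb. The effect on type is indirect and may be nil. The primary endpoint, prevalence of anemia at recruitment, does not use the score and is untouched. This is a weakness in secondary analyses that is worth correcting, not a flaw in the main result.

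**What to change.** - In section 8.2, name the CDAI version and record its hematocrit item separately from the total. Alternatively, state that the item will be derived from the baseline blood count; this requires keeping the hematocrit value that entered the score.
- In section 10, state that the CDAI without that item, as a continuous score, is used when activity is related to severity of anemia and when models of anemia are adjusted for activity.
- Report the same analyses with the full CDAI alongside as a sensitivity analysis. There is no need to restrict the full score to descriptive use everywhere.
- Name the CAI version, and apply the same rule if it contains hemoglobin.

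The cost is a few lines of protocol text and at most one extra data field, with no new test or visit. The downside is small: the reduced score has no established cut-off, hence its use as a continuous variable.

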8.3 Study assessments

8.3.1 Timing of assessments

Follow-up will be performed at weeks 4, 12 and 24 . The following data are to be recorded:

- a) Physical examination
- b) Adverse Event Review
- c) Weight in Kg
- e) Full blood count
- f) Biochemical series
- g) IBDQ score, VAS evaluation of fatigue
- h) Actual treatment

8.4 Long-Term Follow-up Assessments

After the end of the study patients will be followed-up as usual for patients with their conditions. Telephone calls will be used to contact patients if visits or data collection time-points are missed; whenever data collection will be impossible, the patient will be identified as 'lost to follow-up'.

8.5 End of Study Participation

Patients will be expected to return to normal standard of care following their participation in the study.

8.6 Schedule of Assessments

A format of all study-related assessments is included in the CRF.

9 Evaluation of Results (Definitions and response/evaluation of outcome measures)

The primary end-point of the observational study (prevalence of anemia) will be evaluated at patient recruitment. Other informations concerning laboratory parameters, quality of life and clinical course will be collected at the scheduled follow-up visits.

10 Statistical methods and number of Subjects to be enrolled

If at least 60 IG-IBD Centers will participate to the study, 5000 to 8000 IBD patients will be screened for anemia within 6 to 12 months from the start of the study. Since anemia affects 25% to 40% of IBD patients, we expect to include 2,000 anemic patients for this observational study. For the first endpoint (the prevalence of anemia) the precision that can be obtained, based on this hypothesis, is summarized in Table 2. Approximately 80 to 90% of these patients will have some form of iron deficiency and/or AI. This will allow to evaluate differences in prevalence of IDA and AI according to gender, age, diagnosis, time from diagnosis, presence of inflammation, disease activity, extension and behavior, and to evaluate variables associated with type and severity of anemia in both univariate and multivariate analysis.

Multivariable models will be fitted to assess the role of anemia on the outcome, while adjusting for potential confounders. Linear regression, logistic regression or Poisson regression models will be used depending on the outcome distributions. Descriptive statistics will be computed overall and by anemia groups.

11 Definition of the end of the study

The competent authority and Ethics Committee will be notified of the end of the clinical study within 90 days of its completion. The end of study will be the date of the last patient's last visit.

12 Data handling and record keeping**13.1 CRF**

All data will be transferred into a Case Report Form (CRF) which will be coded. The investigator will maintain separately a logbook with patient ID and corresponding code. All study data in the CRF will be extracted from and be consistent with the relevant source documents. The CRFs will be completed, dated and signed by the investigator or designee in a timely manner. It remains the responsibility of the investigator for the timing, completeness, legibility and accuracy of the CRF pages. The CRF will be accessible to study coordinators, data managers, the investigators, Auditors and Inspectors as required.

CRFs will be emailed to the study coordination centre (Fondazione IRCCS Policlinico San Matteo, Pavia).

The investigator will retain a copy of each CRF page at site. The investigator will also supply the study coordination Center with any required, anonymised background information from the medical records as required.

The investigators must ensure that the CRFs and other trial related documentation is sent to the trial coordination Center containing no patient identifiable data.

Completed CRF data should be entered into the database within 2 months of the pages being completed/or patient visit being completed.

The investigator will retain all copies of the CRF in the relevant sections of their Investigator Site File with any required coded background information from the medical records as required.

All CRF pages must be clear, legible and completed in black ink.

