5.4 Participants Study duration

Expected duration of subject participation to both the observational and the therapeutic trials will be 24 weeks; all anemic patients recruited in the study will undergo screening to investigate the mechanism of anemia, and follow-up evaluation will be performed at weeks 4, 12 and 24. At follow-up, informations about the treatment of anemia, fatigue and quality of life must be collected.

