5.6 Study Outcome Measures

5.6.1 Primary outcome measure

The primary outcome will be computed as the ratio of the number of anemic patients over the number of patients screened for anemia together with its 95% confidence interval.

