5.6.2 Secondary outcome measure

1. Relative prevalence of IDA and AI in IBD will be computed as the ratio between the number of patients with IDA or with AI over the total number of anemic patients
2. Influence of anemia on fatigue and quality of life among IBD patients. Quality of life will be evaluated using the validated Italian translation of the Inflammatory Bowel Disease Questionnaire (IBDQ, Cicciocioppo et al, 2011), whereas the effect of anemia on fatigue will be measured using a Visual Analogue Scale.
3. Influence of anemia on hospitalizations, additional outpatient visits, number of endoscopic examinations and further treatments will be assessed through the analysis of correlations between the degree of anemia and the relevant parameters.

6 Selection and withdrawal of subjects

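### Poisson regression is the only count model named for the adjusted analyses; with its usual standard errors, overdispersed hospitalization, visit and endoscopy counts would get intervals that are too narrow

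*Protocol*

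**What the plan says.** Section 10 sets out the adjusted analyses in two sentences: "Multivariable models will be fitted to assess the role of anemia on the outcome, while adjusting for potential confounders", followed by "Linear regression, logistic regression or Poisson regression models will be used depending on the outcome distributions". The outcome is not named, and nothing is said about the variance estimator or about overdispersion.

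The count outcomes appear in section 5.6.2, item 3: "Influence of anemia on hospitalizations, additional outpatient visits, number of endoscopic examinations and further treatments will be assessed", and the sentence goes on "through the analysis of correlations between the degree of anemia and the relevant parameters". Poisson regression is not mentioned there. Table 1 lists the same items under the third secondary objective.

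On size and follow-up, section 10 states "we expect to include 2,000 anemic patients for this observational study", and section 5.4 states "Expected duration of subject participation to both the observational and the therapeutic trials will be 24 weeks". A 95% interval is specified only for the primary outcome (section 5.6.1, "together with its 95% confidence interval"). No significance level, event rate or dispersion is given for the counts.

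**The concern.** Of the three models listed, Poisson is the only one made for counts, and the counts in section 5.6.2 item 3 are its only evident use. The IBDQ and VAS scores suit linear regression, and the proportions suit logistic regression.

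A Poisson model with model-based standard errors takes the variance to equal the mean among patients with the same covariates. The design makes this unlikely. There are no exclusion criteria (section 6.1), at least 60 centers take part (section 5.2), Crohn's disease and ulcerative colitis are both included (section 8.2), any IBD treatment is allowed (section 7), and some patients may be lost to follow-up (section 8.4). Adjustment will absorb only part of the resulting variation in event rates.

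At stake is the reported precision of the associations between degree of anemia and resource use. Standard errors that leave out the extra variation give intervals that cover too rarely and tests that reject too often.

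**Working it through.** **The plan's own figures.** The only statistical calculation in the protocol is Table 2, on prevalence. With p ± 1.96·√(p(1−p)/n) it reproduces: 23.8–26.2 (5000 at 25%), 38.64–41.36 (5000 at 40%; width 2.72, the stated 2.8 being the difference of the rounded limits), 24.05–25.95 (8000 at 25%) and 38.93–41.07 (8000 at 40%). There is no figure for the counts to reproduce.

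**Inputs.** From the protocol: 2000 anemic patients. Assumed, because the protocol gives none of them: a two-sided 5% level, the mean count μ over follow-up, and the between-patient dispersion a. For gamma-Poisson counts the variance-to-mean ratio is φ = 1 + aμ.

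**Formula.** If the variance is φ times the mean, the model-based standard error is too small by a factor √φ. With no true effect the Wald statistic then has standard deviation √φ, so the true level is 2·[1 − Φ(1.96/√φ)].

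- φ = 1.2: 1.96/1.095 = 1.789, level 7.4%
- φ = 1.5: 1.96/1.225 = 1.600, level 11.0%
- φ = 2: 1.96/1.414 = 1.386, level 16.6%
- φ = 3: 1.96/1.732 = 1.132, level 25.8%

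The level reaches twice nominal at φ = (1.960/1.645)² = 1.42. The formula does not contain N. At φ = 2 the stated intervals are too narrow by a factor of √2 = 1.41.

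**Simulation.** 2000 patients, a continuous hemoglobin covariate with no effect, 4000 replicates per row. Rejection rates in percent:

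| μ | a | φ | Formula | Model-based SE | Sandwich SE | Quasi-Poisson SE |
|---|---|---|---|---|---|---|
| 0.1 | 0 | 1.0 | 5.0 | 4.8 | 5.2 | 4.8 |
| 0.1 | 1 | 1.1 | 6.2 | 5.4 | 4.9 | 4.4 |
| 0.1 | 2 | 1.2 | 7.4 | 7.1 | 5.3 | 4.9 |
| 0.2 | 1 | 1.2 | 7.4 | 7.2 | 4.8 | 4.8 |
| 0.5 | 1 | 1.5 | 11.0 | 10.4 | 5.2 | 5.0 |
| 0.5 | 2 | 2.0 | 16.6 | 17.0 | 5.0 | 4.9 |
| 1 | 1 | 2.0 | 16.6 | 16.1 | 5.1 | 5.2 |
| 2 | 1 | 3.0 | 25.8 | 25.6 | 5.1 | 5.2 |

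The Monte Carlo standard error at 5% is √(0.05·0.95/4000) = 0.34 percentage points, so the corrected columns agree with 5%. The mean estimated log rate ratio lay between −0.0009 and 0.0019: the estimate is not biased, and only its standard error is wrong. Negative binomial regression was not part of this simulation. Patients were taken as independent, so correlation within centers is not covered.

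**The case against.** The strongest reply has four parts.

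1. **The protocol does not assign Poisson regression to these outcomes.** Section 5.6.2 names correlations, and section 10 lets the model follow the distribution. This stands: the link is an inference. It is a reasonable one, since section 10 is the only place that describes adjusted analyses and Poisson has no other evident use. The two sections still need to be brought into line.

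2. **Naming Poisson regression fixes a model family, not a variance estimator.** This also stands. Robust or quasi-Poisson standard errors fit the present wording, and linear regression, or logistic regression on any versus no event, remains open. But nothing requires any of these, and model-based errors are the usual implementation.

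3. **Such detail belongs in the SAP, which is not shown.** Silence on the variance estimator is therefore no error in itself. What remains is that the protocol chose to list its models, and that the one count model listed is fragile in this population unless qualified.

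4. **The size is assumed.** This stands in full. With an assumed mean of 0.1 hospitalizations in 24 weeks and a of 1 to 2, the simulated level is only 5.4% to 7.1%. Levels of about 16% to 26% need means of about 0.5 to 2 with substantial heterogeneity left after adjustment.

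**Conclusion.** The point holds in conditional form. If Poisson regression is applied to these three counts with model-based standard errors, and if they are overdispersed given the covariates, intervals will be too narrow and p-values too small. At a nominal 5% the true level is about 5–7% for rare counts with little heterogeneity, 11% at a variance-to-mean ratio of 1.5, 16.6% at 2 and 25.8% at 3. Overdispersion is likely from the design, but its amount cannot be taken from the document.

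A reader might infer more, and the document does not support it:

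- That the false-positive rate is well above 5% as a matter of fact. No event rate, dispersion, significance level or variance estimator is stated.
- That overdispersion creates an apparent effect of anemia in the sense of bias. The rate ratio stays centered on the truth; the fault is false precision.
- That 2000 patients make the problem worse. The inflation does not depend on N.
- That a planned economic paper would rest on these results. Section 19 merely leaves such a paper open.

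The primary endpoint is untouched. It is a proportion, and section 9 says "The primary end-point of the observational study (prevalence of anemia) will be evaluated at patient recruitment". This is a minor improvement to a secondary analysis.

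**What to change.** In section 10, state that hospitalizations, additional outpatient visits and endoscopic examinations will be analyzed by Poisson regression with robust (sandwich) standard errors, or by negative binomial regression. Make this the default, fixed in advance, and not a choice that waits for a dispersion test. Reword section 5.6.2 item 3 so that it points to this adjusted model, or says how the correlations it names relate to it.

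The cost is a sentence in each section and one software option, with no new data. Estimates keep their meaning as rate ratios. The downside is wider intervals when overdispersion is present, by about √φ (1.22 times at a ratio of 1.5, 1.41 times at 2), which is the width they should have had. When it is absent, almost nothing changes.
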